# **Protocol Information**

Protocol title	Evaluation of the Clinical Impact and Safety of Focused Transesophageal Echocardiography During Resuscitation of Critically Ill Patients in the Emergency Department and Intensive Care Settings
Short Title	Focused TEE in Critically-ill patients
Brief description of the protocol	The general objective of this study is to evaluate the clinical impact and safety of transesophageal echocardiography (TEE) used during the evaluation of critically-ill patients in the emergency and intensive care settings. The target population for this study are critically-ill patients over the age of 18 who as part of their routine clinical care are receiving a focused TEE. There are no interventions, outside those that represent standard clinical care, as part of this study.
Resubmission*	No
Application type	EXPEDITED Category 5
Approval and Expiration	Approval: November 24, 2020 Expiration: December 1, 2021 *Intention to request extension of approval

# **Overall objectives**

The primary objective of this study is to determine the **clinical impact** and **safety** of transesophageal echocardiography (TEE) performed during the evaluation of critically-ill patients in the **emergency department** and **intensive care settings**.

The secondary objective(s) of this study are to **characterize the use of this imaging modality** in the subsets of critically-ill patients in **shock and cardiac arrest**; including but not limited to; description of the frequency of studies, clinical indications, clinician characteristics, echocardiography findings, timing of studies, procedure-related complications and patient outcomes.

### Background

Goal-directed transesophageal echocardiography (TEE) is frequently used by physicians caring for intubated critically-ill patients as a reliable imaging modality that is well-suited to answer questions at bedside.

While in most patients, transthoracic echocardiography (TTE) can provide the information needed, there are situations in which goal-directed transesophageal echocardiography (TEE) provides superior diagnostic value. In contrast with comprehensive echocardiography, TEE

provides acute care clinicians with a goal-directed framework to guide clinical care at the pointof-care in various clinical scenarios. Common applications of TEE in critically-ill patients include assessment of circulatory failure, hemodynamic monitoring, evaluation of unexplained hypoxemia, procedural guidance and cardiac arrest.

Over the last decade, a small number of studies have demonstrated the feasibility and clinical impact of TEE in different acute care settings, including the emergency department and intensive care units.

In both of these settings, **retrospective studies** of focused TEE have demonstrated this modality to be clinically impactful in the diagnostic evaluation of patients in shock, hemodynamic monitoring in patients with circulatory failure, in the evaluation of fluid responsiveness to guide fluid therapy, and in the guidance of procedures such as percutaneous mechanical circulatory support.

Specifically in the emergency department setting, one small prospective observational study evaluating the use of TEE during resuscitation, has shown that traditional chest compressions following external landmarks as recommended by guidelines, resulted in an AMC located over the ascending thoracic aorta, or left ventricular outflow tract in over 50% of patients, suggesting that compressions over the center of the heart may actually impede some of the potential forward blood flow in a significant portion of patients. Most recently animal models of cardiac arrest have demonstrated that chest compressions performed directly over the LV rather than the center of the chest result in improved aortic pressures, ETCO2, and survival.

While the above-mentioned studies have provided some promising data on the utility of this emerging modality, to date only small single center and retrospective studies have evaluated the clinical impact of focused TEE in resuscitative settings. Furthermore, no studies have investigated the safety of this imaging modality, specifically in the population of emergency department patients. The proposed study has the potential to substantially improve our understanding of the clinical impact and the safety of TEE in emergency and critical care applications.

# **Study Design**

### Design

We plan to conduct a prospective observational study involving a convenient sample of patients receiving a TEE as part of their clinical care in emergency department (ED) and intensive care unit (ICU) settings. The study will enroll adult patients receiving focused TEE as part of their routine care for the most common clinical indications of focused TEE in critical care patients in ED and ICU settings including: 1. Evaluation of intra-arrest and post cardiac arrest in inhospital (IHCA) and out-of-hospital cardiac arrest (OHCA), 2. Evaluation of patients in shock, 3. Hemodynamic monitoring, and 4. Procedural guidance.

Data will be collected from the patients' electronic medical record (EMR) and EMS run-sheets in the case of OHCA cases. Transesophageal echocardiography (TEE) images routinely recorded for quality assurance and as part of standard clinical care, will be collected. Patients will be

enrolled in the study by clinicians participating from their care who are involved in the performance of TEE. Following identification of eligibility criteria by the enrolling clinician, a RedCap data collection instrument will be used to prospectively gather basic demographics, and clinical data, including the indication for the TEE (i.e. including intra-arrest or post arrest, evaluation of shock, hemodynamic monitoring or procedural guidance), operator findings on the TEE, probe insertion procedure details, TEE views obtained during the study, clinician's interpretation of the images, change in management (if any) as a result of the information provided by TEE. Procedure-related immediate complications, and outcomes when indicated.

Minimal patient demographic information to be collected including: age, gender, and BMI. In the case of cardiac arrests, when applicable the following information will be collected: if the arrest was witnessed, location of arrest, if bystander CPR was performed, will be obtained from the EMR and EMS run sheets. Identification of certain disease states in the medical history patients such as coronary artery disease, congestive heart failure, chronic kidney disease, diabetes mellitus, hypertension, previous STEMI, ventricular assist device, and implantable cardioverterdefibrillator will also be obtained from the EMR and prospectively entered to the RedCap data form. For cases of OHCA, data collection will also include an analysis of pre-hospital care to examine the following factors (Ustein Cardiac Arrest Variables); estimated time of arrest, response time, EMS interventions (chest compressions, defibrillation, airway procedures, dosing and timing of drug administration). For all cardiac arrest cases, information collected will also include time of arrest, ED arrival time in case of OHCA, time to first image of TEE, time of first rhythm, and times and type of intervention (mechanical CPR, arterial line, epi administration, etc.) The study of patient outcomes will be specific to the clinical indication and will include ROSC, survival to hospitalization and discharge in OHCA. In cardiac arrest cases, additional factors pertaining CPR physiology will be examined.

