#### **Analysis Plan**

Baseline and demographic characteristics will be summarized by standard descriptive statistics (including mean and standard deviation for continuous variables such as age and standard percentages for categorical variables such as gender). Continuous variables will be analyzed using Student's t-test, categorical data using Chi-square. Descriptive statistics will be presented as a mean with standard deviation, or as a median with an interquartile range. Differences in patient characteristics will be analyzed using  $\chi^2$  testing, Student's t-test, or the Mann-Whitney U test, as appropriate. We will provide frequencies with their binomial 95% confidence intervals for descriptive purposes. For bivariate or multivariable analyses, we will use logistic regression, ANOVA, or chi-squared testing, as appropriate. Statistical methods will be performed in statistical software (STATA).

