#### Sample size:

Consistent with the descriptive nature of this study, our intention is to capture as many TEEs as possible within those performed across the clinical indications of interest for this study. Based on

prior research and Quality Assurance data, over the period of one year, we estimate a total of approximately 100 studies to be performed and analyzed as part of this study.

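### The protocol fixes a clinician-entered convenience sample and plans no comparison of TEEs entered with TEEs performed, so any selection bias in the change-in-management and complication frequencies would go unmeasured

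*Protocol*

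**What the plan says.** The Design section of the protocol sets out a "prospective observational study involving a convenient sample of patients receiving a TEE as part of their clinical care". Patients are "enrolled in the study by clinicians participating from their care who are involved in the performance of TEE". The clinician's eligibility check comes first and opens the record: "Following identification of eligibility criteria by the enrolling clinician, a RedCap data collection instrument will be used to prospectively gather basic demographics". The same form takes the two items that serve the primary objective (Overall objectives: clinical impact and safety), namely "change in management (if any) as a result of the information provided by TEE" and "Procedure-related immediate complications, and outcomes when indicated".

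The Sample size section states the aim on completeness: "our intention is to capture as many TEEs as possible within those performed across the clinical indications of interest for this study". From "prior research and Quality Assurance data, over the period of one year, we estimate a total of approximately 100 studies" it forecasts the yield, using that one figure for studies performed and studies analyzed alike.

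The Analysis Plan says "We will provide frequencies with their binomial 95% confidence intervals for descriptive purposes".

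The Design and Procedures sections also say that TEE images are routinely stored for quality assurance and that patient charts will be used for data entry. Neither source is given the task of finding TEEs that were performed but not entered.

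**The concern.** In a descriptive study the reported frequency is itself the result, so it matters which TEEs are counted. Here the clinicians involved in the procedure also decide whether the case is entered, and the protocol plans no comparison of entered with performed cases. Entry could plausibly depend on how the TEE went. A striking change in management might prompt entry, while a difficult or hurried case might be left out or, equally, be more likely to be recorded. The documents do not settle the direction.

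At stake are both measures behind the primary objective. The Background says that safety has not been studied in emergency department patients, and the Potential Study Benefits section says that the results may contribute to guidelines. A reader of the results would want to know what share of the performed TEEs the frequencies describe.

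**Working it through.** **The plan's own figure.** The figure of about 100 TEEs in a year is a feasibility estimate. The counts behind it are not given, so there is nothing to recompute. The documents state no capture share, no expected change-in-management rate and no expected complication rate. Every rate below is therefore an assumption, shown over a range.

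**Formula.** Let c be the share of performed TEEs that are entered, p_e the rate among entered TEEs and p_m the rate among missed TEEs.

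- Rate over all performed TEEs = c x p_e + (1 - c) x p_m
- Bias of the reported rate = (1 - c) x (p_e - p_m)

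The bias is a product: if either factor is zero, there is none.

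**Change in management.** Assume 100 entered TEEs and p_e = 60%. The exact (Clopper-Pearson) 95% interval at 60/100 is 49.7% to 69.7%. Coverage is the probability that the exact interval, computed from a binomial count with n = 100 and rate 0.60, contains the rate over all performed TEEs. With no bias it is 95.8%. The paired entries are for missed cases having the lower and the higher rate.

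| Share entered | Difference (points) | Rate over all TEEs | Coverage |
|---|---|---|---|
| 90% | 10 | 59% / 61% | 96.5% / 95.8% |
| 90% | 20 | 58% / 62% | 95.4% / 94.9% |
| 90% | 30 | 57% / 63% | 93.5% / 93.2% |
| 80% | 10 | 58% / 62% | 95.4% / 94.9% |
| 80% | 20 | 56% / 64% | 90.7% / 90.5% |
| 80% | 30 | 54% / 66% | 82.0% / 76.3% |
| 70% | 10 | 57% / 63% | 93.5% / 93.2% |
| 70% | 20 | 54% / 66% | 82.0% / 76.3% |
| 70% | 30 | 51% / 69% | 61.8% / 54.3% |

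Example: at 80% entry and a 20-point lower rate in missed cases, 0.8 x 60% + 0.2 x 40% = 56%, a bias of 0.2 x 20 = 4 points.

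**Complications.** Assume a true rate of 4% over all performed TEEs, 80% entry and 100 entered. Let complicated TEEs be entered r times as often as the others.

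| r | Entered: complicated / other | Expected rate among entered | Coverage of 4% |
|---|---|---|---|
| 0.5 | 40.8% / 81.6% | 2.04% | 87.3% |
| 0.8 | 64.5% / 80.6% | 3.23% | 95.7% |
| 1 | 80% / 80% | 4% | 96.4% |
| 1.25 | 99.0% / 79.2% | 4.95% | 93.4% |

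For a rare event, a modest absolute difference can be a large relative one. At r = 0.5 the missed cases have a rate of 0.04 x (1 - 0.408) / 0.2 = 11.8%, about 10 points above the entered cases, and the estimate is halved. At an assumed true rate of 2% and r = 0.5, the expected estimate again halves, to 1.01%, but the interval is so wide relative to the rate that coverage stays at 99.9%.

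**What a known share would allow.** If c is known, worst-case bounds follow: lower = c x p_e, upper = c x p_e + (1 - c). At c = 80% and an assumed 70% change in management, these are 0.8 x 70% = 56% and 56% + 20% = 76%. At an assumed 2% complications they are 1.6% and 21.6%. The upper complication bound requires every missed TEE to be complicated, so it is a limit and not a likely value.

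**The case against.** Four things can be said in the plan's favour.

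- **The intention may be near-complete capture.** The Sample size section wants as many TEEs as possible and gives one number for performed and analyzed. Its phrase about those performed can be read as a restriction to the listed indications. This is a fair reading, and it makes high capture plausible. It remains an intention, though. It does not make the sample consecutive, it sits awkwardly beside a convenience sample, and no step is planned to confirm it.
- **The number performed could be counted later.** A reader might infer that the count is lost for good. The documents do not support that: stored clips and charts exist, and quality-assurance data have already served to forecast volume. What is missing is the commitment to use them. The choice of a convenience sample, by contrast, is fixed in the protocol and is not a detail left to an analysis plan.
- **The share entered does not by itself settle the matter.** This is correct. The bias also depends on the difference between entered and missed cases, so knowing the share bounds the bias without measuring it.
- **The study is openly descriptive.** The sample type is declared, the intervals are offered for descriptive purposes, and no threshold is at risk. This lowers the stakes, but declaring the sample type does not tell a reader how large its effect is.

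**Conclusion.** The point holds as a cheap improvement to a stated design choice. Clinicians involved in the TEE decide which cases are entered, and the protocol plans neither consecutive enrolment nor a check of entered against performed TEEs. Any resulting bias reaches both frequencies behind the primary objective and is not reflected in their confidence intervals.

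Under the assumptions used here (100 entered, 60% change in management), the effect is negligible at high capture or with small differences. It becomes material only when capture is about 80% or lower and the difference is about 20 points or more. Complications need a separate reading because relative distortion matters: at 80% entry, a halved chance of entry for complicated cases halves the estimate, whereas entry ratios of 0.8 and 1.25 leave coverage at about 96% and 93%.

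A reader might go further and infer that the frequencies are biased in a known direction, for example towards impressive or uncomplicated cases. The documents give neither the share entered nor the difference, so they support no sign and no size.

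**What to change.** In the Design section, replace the convenience sample with consecutive enrolment of all eligible focused TEEs in the study period. Then:

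1. Compare REDCap periodically with the quality-assurance clip archive and the medical records already held.
2. Report the number entered over the number performed.
3. For missed cases, abstract at least the indication and any documented complication, and report them separately from the prospectively entered cases.

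The cost is a wording change, a periodic list comparison and some abstraction. With 100 entered, the missed cases number 100/c - 100: about 11, 25 or 43 at 90%, 80% or 70% entry. No patient procedure changes.

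The limits should be stated. Clinician-stated change in management will often be missing for late-added cases, so it needs its own denominator. Charts may under-record complications. TEE attempts without stored clips, such as failed insertions, may escape the quality-assurance list. The bias is therefore bounded rather than removed.

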#### Procedures

There are no interventions or procedures in this study. As part of this study, we are not proposing any manipulation to the subject's clinical environment, therefore any procedures or surgical interventions that take place during the clinical encounter in which TEE is being performed, are being performed as part of standard clinical care and in the interest of the patient rather than for study purposes.

We will be entering previously described clinical data into REDCap from EPIC patient charts. The TEE ultrasound clips that are routinely stored for quality assurance will be reviewed, analyzed, and qualitative data will be extracted. All of the data will be analyzed retrospectively from standard of care procedures. Follow-up, beyond hospital discharge of subjects will not occur.

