#### **Potential Study Risks**

Given the design as an observational protocol, there are no interventions as part of this study. As explained before, all the interventions such as procedures occurring during this protocol are the standard clinical practice and their use will be directed by the treating physicians as part of the standard care.

Radioisotopes/radiation-producing machines (e.g., X-rays, CT scans, fluoroscopy) and associated risks: No radioisotopes or radiation-producing machines will be used during the protocol.

Physical well-being: Participation in this study will not incur any additional risk to subjects' physical well being beyond what would be experienced during standard care. Psychological well-being: Participation in this study will not incur any additional risk to subjects' psychological well being beyond what would be experienced during standard care. Economic well-being. Participation in this study will not incur any additional risk to subjects' economic well being beyond what would be experienced during standard care. Social well-being. Participation in this study will not incur any additional risk to subjects' economic well being beyond what would be experienced during standard care. Social well-being. Participation in this study will not incur any additional risk to subjects' social well being beyond what would be experienced during standard care. Social well being beyond what would be experienced during standard care. Social well being beyond what would be experienced during standard care. Social well being beyond what would be experienced during standard care. Although the risk of mortality in our patient population is high (approximately 90%), the risk of the observations made in this study are minimal as all observations are currently being recorded as part of standard of care. All laptops, desktops, and mobile devices used to access, transmit, or store Prohibited or Restricted Data as defined under the Data Classification Guidelines are encrypted. We will make sure that any new device used in this study will be encrypted prior to use.

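### Safety is part of the primary objective, but an event counts as a complication only if it is labelled procedure-related, with no assessor named and no all-cause event list

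*Protocol*

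**What the plan says.** Protocol, Overall objectives: the primary objective covers the clinical impact and the safety of TEE. No safety variable is named there. The nearest item, "procedure-related complications and patient outcomes", appears under the secondary, descriptive objective.

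Protocol, Design: the data items end with "Procedure-related immediate complications, and outcomes when indicated". Neither procedure-related nor immediate is defined. Patients are "enrolled in the study by clinicians participating from their care who are involved in the performance of TEE". The form follows from that step: "Following identification of eligibility criteria by the enrolling clinician, a RedCap data collection instrument will be used to prospectively gather basic demographics, and clinical data".

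Protocol, Design and Procedures: there is a second source, since "Data will be collected from the patients' electronic medical record (EMR) and EMS run-sheets in the case of OHCA cases". Chart entry is tied to what the protocol has already listed: "We will be entering previously described clinical data into REDCap from EPIC patient charts". The only later review described is of stored ultrasound clips.

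Protocol, Analysis Plan and Sample size: frequencies will carry binomial 95% confidence intervals, and about 100 TEE studies are expected in one year.

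**The concern.** Relatedness is written as a condition for an event to be counted, not as a separate judgement on an event already recorded. That matters most where attribution is hardest. The protocol enrols patients in arrest or shock (along with others who have TEE for monitoring or procedural guidance), and Potential Study Risks puts mortality at about 90%. Hypotension, desaturation, arrhythmia or bleeding around insertion then has a ready explanation other than the probe.

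The Background justifies the study partly by the absence of safety data in emergency department patients. If TEE-caused events are put down to the illness and so not entered as complications, the resulting rate could look more reassuring than it should. Readers could not tell, because the study data would hold nothing to compare it with. This concerns events seen at the bedside during the TEE itself, not the length of follow-up.

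**Working it through.** **The protocol's own figure.** The 100 studies are a volume estimate. No alpha, power, expected complication rate or margin is given, so there is no calculation to reproduce, and none of the results below contradicts a stated figure.

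**What the text collects.** Three checks on the wording:

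- Design names one complication item, restricted to procedure-related immediate events.
- Procedures limits chart entry to data already described. Nothing described is a peri-procedural adverse event recorded regardless of cause.
- Outcomes recorded without attribution are return of circulation and survival, stated for out-of-hospital arrest. These would not reveal oral bleeding, tube displacement or transient hypotension.

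**Dependence on attribution (assumed inputs).** Suppose 10 of 100 TEEs have a new event during or just after insertion. Exact (Clopper-Pearson) 95% intervals:

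- 3 attributed to TEE: 3/100 = 3%, interval 0.6–8.5%.
- All 10 attributed: 10/100 = 10%, interval 4.9–17.6%.

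The second figure is also the all-cause rate. If TEE really caused 3 of the 10, 3% is correct. The range therefore shows sensitivity to labelling and does not measure bias.

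**Direction of error (assumed inputs).** Let p be the true TEE-caused rate, s the share of those events labelled related, b the rate of illness-caused peri-procedural events, and f the share of those wrongly labelled related. Then

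recorded rate = p·s + (1 − p)·b·f.

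- p = 5%, s = 0.50, f = 0: 0.05 × 0.50 = 2.5%.
- p = 5%, s = 0.50, b = 30%, f = 5%: 0.025 + 0.95 × 0.30 × 0.05 = 0.0393, or 3.9%.
- p = 5%, s = 0.50, b = 30%, f = 10%: 0.025 + 0.95 × 0.30 × 0.10 = 0.0535, or 5.4%.

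The rate is too low when p(1 − s) > (1 − p)·b·f, and too high when the inequality is reversed. With p = 5%, s = 0.50 and b = 30%, the balance point is f = 0.025 / 0.285 = 8.8%.

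**What the interval misses.** With p = 5%, s = 0.50 and f = 0, the chance of recording no complication in 100 is 0.975^100 = 8.0%, against 0.95^100 = 0.6% with full capture. A zero count has an exact interval of 0–3.6%, which excludes the true 5%. The binomial interval describes sampling error only.

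**The case against.** The strongest reply is that the filter is read into a phrase. Procedure-related complications can serve simply as a heading for complications around the procedure, and the REDCap form, which is not shown, may already be a checklist. Event definitions are also often left to a form or an SAP. This stands in part: the text does not describe the act of judging relatedness. But the restriction is in the protocol's own data-collection wording, and an SAP cannot restore events that the form did not ask for. If the form is broader, Design should say so.

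Three stronger readings are tempting, and the protocol does not support them.

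- A reader might infer that TEE operators judge their own complications. Design says who enrols, not who completes the complication item, and Procedures points to chart entry by the study team for at least some data. The operator's role is an inference.
- A reader might infer that events attributed to illness are lost for good. The medical record is a named source and may still hold them, and insertion details are collected without a relatedness condition. The supportable statement is that such events may not be recorded as complications in the study data.
- A reader might infer a proven downward bias. Illness events wrongly labelled as related push the rate up, and the sign can reverse.

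It is also fair to say that 90% is a mortality figure, not a peri-procedural event rate, and that mechanical injuries at insertion are harder to blame on the illness than haemodynamic events are.

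**Conclusion.** The point holds as a weakness in how a primary-objective variable is defined. By the text, relatedness decides whether an event counts; no assessor is named, and no event list applies regardless of cause. The consequence is a risk of misclassification. Under-counting is the more plausible direction, because the illness offers an easy alternative explanation, but neither direction nor size can be established from the protocol. The illustrative 3% and 10% rest wholly on an assumed 10 events per 100 TEEs and an assumed attribution share of 30% to 100%. The reversal of sign rests on assumed values of p, s, b and f. The weakness should be corrected, and it does not invalidate a descriptive study. Error in either direction calls for the same remedy, since it can be seen only if events are recorded before they are attributed.

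**What to change.** In Design, replace the complication item with a short yes/no list of prespecified events from the start of probe insertion to probe removal, recorded regardless of presumed cause. Examples are oropharyngeal or gastrointestinal bleeding, dental or oral injury, airway-device displacement, new desaturation, and new hypotension or arrhythmia in patients not in arrest. Add a separate relatedness field and state which role completes it. Report the all-cause peri-procedural rate and the rate judged related, each with its interval, with arrest and non-arrest patients shown separately.

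The cost is a few REDCap fields and a sentence or two in the protocol, with no extra staff and no change to care. The downside is that the all-cause rate includes events due to the illness, will look less favourable, and in an uncontrolled series cannot by itself be read as harm from TEE. It must therefore be shown beside the related rate. A relatedness field completed by the same clinician would still be a judgement, but it would be visible and open to re-assessment.

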#### **Study duration**

The expected duration of the study is 1 year. The relevant dates are data collected from December 1st, 2020 to December 1st, 2021.

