# **Target population**

Adult patients who as part of their routine clinical care receive focused TEE in the emergency department of intensive care setting. Children (age under 18 years) will not be eligible for inclusion in this study.

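### Will ROSC and survival to hospitalization in OHCA be inflated by patients who had already reached those outcomes before TEE?

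*Protocol*

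**What the plan says.** The Design section names the outcomes in one sentence: "The study of patient outcomes will be specific to the clinical indication and will include ROSC, survival to hospitalization and discharge in OHCA". It does not say which OHCA patients form the denominator of each rate.

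The first of the four enrolled indications in the same section is "Evaluation of intra-arrest and post cardiac arrest in inhospital (IHCA) and out-of-hospital cardiac arrest (OHCA"), so scans during and after an arrest share one numbered item. The description of the REDCap form is finer. There the indication is recorded with the categories "including intra-arrest or post arrest, evaluation of shock, hemodynamic monitoring or procedural guidance", and outcomes are collected where they apply.

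For all cardiac arrest cases the times to be abstracted include "time of arrest, ED arrival time in case of OHCA, time to first image of TEE, time of first rhythm", together with the times of interventions. Neither the time of ROSC nor the time of admission is named. Target population confirms that patients may "receive focused TEE in the emergency department of intensive care setting", so some OHCA patients will be inpatients when scanned.

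Two statements bear on how long outcomes are tracked. Study duration says: "The relevant dates are data collected from December 1st, 2020 to December 1st, 2021". Procedures says: "Follow-up, beyond hospital discharge of subjects will not occur".

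**The concern.** An outcome rate is easiest to interpret when everyone in the denominator could still have, or fail to have, the outcome when the clock starts. Here the natural start is the TEE. A post-arrest patient has in general already regained circulation, so for that patient ROSC is closer to an entry condition than an outcome. An OHCA patient scanned in the ICU has likewise already survived to hospitalization. The two groups differ, because a post-arrest patient still in the ED has had ROSC but may yet die before admission.

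The outcome sentence speaks of OHCA as a whole, and the numbered indication joins intra-arrest with post-arrest scans. A reader can therefore imagine one ROSC percentage over all OHCA patients. That figure would move with the share of late scans, could not be compared with rates from intra-arrest TEE, and would carry a binomial interval suggesting more meaning than it has. Potential Study Benefits hopes that the results will inform guidelines, so a misread rate could matter.

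A smaller worry is that, if 1 December 2021 ended all data collection, patients still in hospital on that day would have no discharge status.

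**Working it through.** **Is there a figure to reproduce?** No. The Protocol states no ROSC rate, no rate of survival to hospitalization and no number of OHCA cases. Sample size gives about 100 studies over all indications, as a feasibility estimate. Potential Study Risks gives mortality of about 90%, which is neither a ROSC rate nor an admission rate and cannot serve as p below.

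**What pooling would do.** Let f be the share of pooled patients who had already met the outcome at TEE, and p the rate among the rest.

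- Pooled rate = f × 1 + (1 - f) × p = p + f(1 - p)
- Excess over the at-risk rate = f(1 - p)

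Both inputs are assumptions:

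| p | f | Pooled rate | Excess |
|---|---|---|---|
| 0.10 | 0.5 | 0.55 | 0.45 |
| 0.20 | 0.2 | 0.36 | 0.16 |
| 0.30 | 0.2 | 0.44 | 0.14 |
| 0.30 | 0.3 | 0.51 | 0.21 |
| 0.30 | 0.5 | 0.65 | 0.35 |
| 0.50 | 0.1 | 0.55 | 0.05 |

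With f and p each between 0.1 and 0.5, the excess runs from 5 to 45 percentage points.

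A worked case shows the scale. Assume 40 OHCA TEEs, 12 of them post-arrest, with ROSC in 8 of the other 28. Pooled, the rate is (12 + 8)/40 = 50% (exact 95% CI 34% to 66%). Among those at risk it is 8/28 = 29% (13% to 49%). The identity agrees: f = 12/40 = 0.30 and p = 0.286, so f(1 - p) = 0.30 × 0.714 = 0.214, and 50.0% - 28.6% = 21.4 points.

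**Does the text lead there?** Apply the identity within the recorded categories.

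- *ROSC, intra-arrest TEEs.* Nobody has yet met the outcome, so f = 0 and the excess is 0 × (1 - p) = 0.
- *ROSC, post-arrest TEEs.* f is about 1, so the rate is about 100% by construction. No analyst would present that as a result of TEE.
- *Survival to hospitalization.* The intra-arrest/post-arrest field is not enough, because post-arrest patients may be in the ED or already admitted. Admission status at TEE is needed. The time to first TEE image is collected and the charts are the data source, so comparing TEE time with admission time in the record settles it.
- *Survival to discharge.* Patients scanned in the ED or ICU have not been discharged, so this form of inflation does not arise.

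**The end date.** At 100 TEEs a year, 100/52 = 1.92 a week, or 7.7 in an assumed 4-week window. At 10% survival that is 0.77 survivors. If only those survivors were lost, survival to discharge would move from 10% to (10 - 0.77)/(100 - 0.77) = 9.3%. This uses all indications and the overall mortality figure, whereas the Protocol names survival to discharge for OHCA, so it indicates order of size only.

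**The case for a change.** The strongest case for a change is that the phrase about indication does not by itself separate the patients. If the indication means the numbered item, reporting by indication still pools scans during and after arrest. The form distinguishes the two, but no sentence links that field to an outcome denominator. For survival to hospitalization the field would not suffice anyway. A statistical analysis plan can choose a denominator only if the data that define it were collected, and neither ROSC time nor admission time is on the list. One sentence and two chart fields would close the gap.

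Part of this stands. The denominator is unwritten, the algebra is exact, and a pooled rate read as what followed TEE would mislead.

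The rest is weaker. The case depends on an analysis that the Protocol does not state. The data-capture wording separates intra-arrest from post-arrest, and there would be little reason to record the distinction without using it. The list of times is open-ended: it is introduced as additional information, and its interventions end in etc. Overall objectives also names the timing of studies among the things to be described. With charts as the source, an unnamed timestamp is not an unavailable one.

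Nor is a whole-cohort proportion wrong in itself. The study has no comparator and calls itself descriptive, and outcomes fall under its secondary objective. The share of all OHCA patients receiving TEE who had ROSC is a legitimate description of the cohort. It becomes biased only if presented as a consequence of the scan.

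On the end date, Protocol Information gives the same day as the expiry of approval and states an intention to request an extension. Study duration calls one year the expected length, and Procedures implies that patients are followed to discharge. A hard stop is the least natural reading.

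**Conclusion.** The concern identifies a real trap, but not an error in this Protocol. The text can be followed to sound rates: ROSC among intra-arrest TEEs, and survival to hospitalization among OHCA patients not yet admitted at TEE. Choosing those denominators is ordinary analysis detail. Only the Protocol is at hand, and a statistical analysis plan may already settle it.

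The possible size, 14 to 35 points at p = 0.30 with f from 0.2 to 0.5, rests wholly on assumed values and on pooling that is nowhere planned. It illustrates the formula and does not predict this study's results. No stated figure is wrong, and the clinical impact and safety aims are unaffected. The end-date point is worth about 0.7 percentage points under its own rough assumptions and falls away given the planned extension. No change follows. The conclusion would differ if a report gave a single pooled OHCA rate and presented it as what happened after TEE.
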